[figure not shown]
¹ The bloc 1 will not be included in the final statistical analysis because is considered as a training bloc. This choice in accordance to the potential biases related to the increase of the sympathetic activity at the beginning of the task caused by a simple moving to action following the resting period.

second session, a short training session of the biofeedback [BFB] technique will be done and the software using for the biofeedback training will be supplied to each participant included in the experimental group to allowed to us to practice BFB by their self at home. The installation of the program and the explanations needed for using it, will be done during the second session (T2). The BFB software (Emwave Pro®) includes a photoplethysmography sensor that can be positioned on the earlobe. The participants will have to practice the biofeedback technique the next 24 days (3X5 min/day).

The period (24 days) between the second session and the third session (T2-T3) will be considered as the intervention period. At the end of the second session (T2), the participants will be separated into two inter-subject groups: an experimental group performing BFB technique (3X5 min per day) in the intervention period (T2-T3) and a control group not performing a specific exercise in the intervention period (T2-T3). The first 40 participants (20 IBS / 20 PNES) will be included into the experimental group (BFB training) whereas the last 10 participants (5 IBS / 5 PNES) will be included into the control group (no training). The participants won't be informed of the condition to which they belong. We will measure the parameters of interest before (T2) and at the end of the intervention period (T3). During the intervention period, all the participants will have to answer to online questionnaires (BVAQ-B, LES, DHS) aiming to examine the psychological profile (alexithymia, traumatic events).

The third session (T3), T2 + 24 days, will be similar of the two previous sessions. We will use the same questionnaires and will record the same electrophysiological parameters. Finally, a debriefing will be done at the end of the session for each participant. The session will be considered as the end of the study visit.

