Concerning the online questionnaires: the package 1 is constituted by the SSQ6, the MAIA-2 and the STAI Y-B. The package 2 is constituted by the Brief-Cope, the BFI-N and the CTQ. The package 3 is constituted by the DHS. The package 4 is constituted by the BVAQ-B and the LE

II : Statistical analysis plan

Independent variables

Analysis A:

The participants will be separated into two inter-subject groups:

- An experimental group performing BFB technique in the intervention phase (T2-T3)
- A control group no performing an exercise in the intervention phase (T2-T3)

The participants won't be informed of the condition to which they belong.

Independent variables

- Measurement time (T1 / T2 / T3) intra-subject
- Group (experimental group / control group) inter-subject

Analysis B:

The participants will be separated into two inter-subject groups performing by a cluster analysis (HF or RMSSD) in the first session (T1):

- A dysfunctional neurovegetative profile (low vagal tone + low vagal flexibility) group
- A functional neurovegetative profile (high vagal tone + high vagal flexibility) group

The participants won't be informed about their neurovegetative profile. We will include all the participants.

Independent variable

- Neurovegetative profile (dysfunctional profile / functional profile) inter-subject

Analysis C:

The participants will be separated into two inter-subject groups performing by a cluster analysis (HF or RMSSD) in the first session (T1):

- A dysfunctional neurovegetative profile (low vagal tone + low vagal flexibility) group
- A functional neurovegetative profile (high vagal tone + high vagal flexibility) group

The participants won't be informed about their neurovegetative profile. We will include only the experimental group performing the BFB technique.

Independent variables

- Neurovegetative profile (dysfunctional profile / functional profile) inter-subject
- Measurement time (T2 / T3) intra-subject

Dependent variables

Physiological variables:

ECG –HRV:

- HF (0.15-0.40 Hz – high frequency) frequency-domain parameter
- LF (0.04-0.15 Hz – low frequency) frequency-domain parameter
- LF-0.1 Hertz (0.075-0.108Hz - spectral power of the low-frequency 0.1Hz band) frequency-domain parameter
- LF/HF (ratio of LF to HF power) frequency-domain parameter
- Total power (total power of the 0-0.40 Hertz band) frequency-domain parameter
- RMSSD (root mean square of successive RR interval differences) temporal-domain parameter

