- SDNN (standard deviation of all NN intervals) temporal-domain parameter
- EDR (ECG-derived-respiration)

GSR (tonic GSR / phasic GSR):

- SCR frequency: number of the spontaneous galvanic skin responses by periods
- SCR amplitude: amplitude of the spontaneous galvanic skin responses by periods
- Integrated skin conductance responses [ISCR]: area of the galvanic skin responses identified on the signal

PPG:

- Pulsatility index variation (PI): Transit time flow

Breathing belt:

- Breathing rate by cycles per minute

EGG:

- Dominant power
- Total power [0-0.15 Hertz]
- Slow-waves frequency per minute

EEG:

- Spontaneous brain rhythms: spectral power of the 0-30 Hertz band

Physiological adaptation to the aversive situation (emotional reactivity task):

HRV, GSR and PPG differences will be calculated to measure the physiological changes causing by the task compared to the resting and the recovery periods. The differences will be calculated as follows:

- Physiological reactivity during the task compared to the resting period (Δ = reactivity HRV – resting HRV / Δ = reactivity GSR – resting GSR / Δ = reactivity PPG – resting PPG)
- Physiological recovery following the task (Δ = recovery HRV – reactivity HRV / Δ = recovery GSR – reactivity GSR / Δ = recovery PPG – reactivity PPG)

- Physiological recovery following the task compared to the resting period (Δ = recovery HRV – resting HRV / Δ = recovery GSR – resting GSR / Δ = recovery PPG – resting PPG)

Psychological variables:

- Alexithymia score (BVAQ-B)
- Neuroticism score (BFI-N)
- Trait anxiety score (STAI Y-B)
- Style of coping (Brief Cope)
- Positive affectivity score (PANAS)
- State anxiety score (STAI Y-A)
- Depressive symptoms score (CES-D)
- Perceived-stress level (PSS)
- Coping flexibility + metacoping scores (CFS + VAS)
- Acceptance score (ICQ-18)
- Social support score (SSQ6)
- Interceptive sensitivity score (MAIA-2)
- Life satisfaction score (SWLS)
- Negative impact scores (LES)
- Frequency, severity and intensity scores (DHS)
- Abuse scores (CTQ)

Statistical analyses

All statistical analyses will be performed using IBM SPSS Statistics®, R software® and JASP®. The alpha value for statistical significance will set at $p<0.05$.

Analyses of the scores collected will be done in several stages:

- Highlighting outlier participants to exclude from our statistical analysis.
- All the conditions for application of statistical tests will be verified.

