- In the case of a failure to respect the conditions for parametric test application, we would make a data transformation to jointly improve normality and homogeneity residues. If the normality is failed and the homogeneity is respected, we would execute non-parametric tests.
- Analysis will be done on the subjects included. Analysis concerning the reactivity period (during the task) will be performed on the all blocs excepted the bloc 1².
- Main and secondary judgment criterions analysis will be performed by parametric tests or by non-parametric tests depending on the conditions for application:

• *Analyse A:*

- An ANOVA to repeated measurement with an intra factor (measurement time: T1 / T2 / T3) and an inter factor (group: experimental / control) on the physiological and psychological data collected.
- Student's test for independent samples will be performed on the psychological scores collected in the second session (T2) to account for the initial level of psychological states between the 2 groups.

² The bloc 1 will not be included in the final statistical analysis because is considered as a training bloc. This choice in accordance to the potential biases related to the increase of the sympathetic activity at the beginning of the task caused by a simple moving to action following the resting period.

- Contrasts will then be made by group on the scores in order to specify the effect of the condition on the physiological and psychological data.
- *Analyse B:*
 - K means non-hierarchical clustering will be performed with K = 2. To categorise participants depending on their resting neurovegetative profile (low vagal tone / high vagal tone) and on their dynamical neurovegetative profile (low vagal flexibility / high vagal flexibility), two K means non-hierarchical clustering will be performed with K = 2. One with HF or RMSSD and one with Δ HF or Δ RMSSD.
 - Student's test for independent samples (dysfunctional neurovegetative profile / functional neurovegetative profile) will be performed on the psychological vulnerability (trait scores) collected.
- *Analyse C:*
 - An ANOVA to repeated measurement with an intra factor (measurement time: T2 / T3) and an inter factor (neurovegetative profile: dysfunctional profile / functional profile) on the physiological and psychological data collected only into the experimental group performing the BFB technique.
- *Correlational analysis:*

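### Outlier participants are removed as the first analysis stage with no criterion and no defined analysis set; at 40 versus 10 the false-positive rate then depends on a rule nobody has fixed

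*Combined protocol and SAP*

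**What the plan says.** Part II of the combined document, under Statistical analyses, opens its list with "Analyses of the scores collected will be done in several stages". The first item is "Highlighting outlier participants to exclude from our statistical analysis". Checking test conditions comes second. Transformation, or non-parametric tests if normality fails, comes third. The next item is "Analysis will be done on the subjects included", with no definition of who is included.

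The only other statement about who is analysed is under Analysis B: "We will include all the participants". Set against Analysis C, which is limited to the experimental group, this most naturally means both groups. It does not say whether outliers stay in.

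Part I fixes the group sizes: "The first 40 participants (20 IBS / 20 PNES) will be included into the experimental group", and the last 10 (5 IBS, 5 PNES) form the untrained control group. Analysis A is a repeated-measures ANOVA with three visits and two groups, at alpha 0.05. The Sample section names HF as the main criterion.

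**The concern.** Whole participants leave the analysis before anyone has looked at distributions or transformed the data. The stages apply to the scores collected, so the natural reading is that a person is an outlier because of outcome values. Four things follow.

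- **Scale.** HF is a spectral power and cannot be negative. If it is right-skewed, screening on the raw scale mainly removes high but genuine values that a log transformation would have accommodated.
- **Error variance.** Trimming each group around its own centre shrinks the within-group variance but leaves chance differences between group means. The error term is then too small and p-values are too low.
- **Imbalance.** Each control removed is 1/10 = 10% of that group; each BFB participant removed is 1/40 = 2.5%.
- **Freedom.** With no variable, threshold, scope or blinding stated, the exclusions could be settled after the group result is known.

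No planned analysis keeps everyone in, so a reader of the results could not see how much the exclusions mattered.

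**Working it through.** **Inputs from the documents:** 40 and 10 participants, three visits, group × time ANOVA, alpha 0.05. The Sample section's subgroup counts do not add up (22 PNES described as 20 plus 5), so the sizes in Part I are used.

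**Assumptions, not in the documents:** HF lognormal with log-SD 0.5 to 1.0, with normal and t (3 df) data for comparison; correlation 0.5 between visits on the underlying normal scale.

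**The plan's own figure.** The plan states no false-positive rate. Its one nearby figure, 22 participants, can be reproduced: f² = 0.12/0.88 = 0.136; with an assumed correlation of 0.5, noncentrality = 0.136 × 22 × 3/0.5 = 18.0 on 2 and 40 df, and power is 0.964 against the required 0.95. It does not bear on this point.

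**Step 1: can a rule reach both groups?** The largest z-score possible in a sample of n is (n−1)/√n. For n = 10 it is 9/3.162 = 2.85; for n = 40 it is 39/6.325 = 6.17. A 3-SD rule applied within group can therefore never remove a control but can remove BFB participants. With skewed data it removes high BFB values only, which shifts the raw BFB mean down by about 0.06–0.10 SD.

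**Step 2: the planned ANOVA under the null.** 3,000 trials per distribution; Monte Carlo SE = √(0.05 × 0.95/3000) = 0.4 points. Rules tried: |z| above 2, 2.5 or 3; boxplot fences at 1.5 or 3 IQR; MAD 2.5 or 3. Each was applied to visit values or to T3−T2 change.

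| Exclusion | Type I error |
|---|---|
| None, all 50 analysed | 4.4–6.2% |
| One fixed rule, pooled, single pass | 4.1–6.4% |
| Within group, single pass, normal | 4.5–7.2% |
| Within group, single pass, t (3 df) | 4.9–8.0% |
| Within group, single pass, lognormal 0.5 | 5.6–11.2% |
| Within group, single pass, lognormal 1.0 | 7.8–17.8% |
| Pooled, repeated until stable | at most 7.4% |
| Within group, repeated until stable | 5.0–31.4% |
| Smallest p over no exclusion and seven pooled rules on one scale | 6.6–17.8% |
| Smallest p over all rules, scales and scopes | 13.6% (normal) to 38.1% (lognormal 1.0) |

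**Step 3: does the later transformation rescue it?** For a two-group t-test at one time point, exclusion on raw values came first, as the SAP orders it, and the test was then run raw or after a log transformation. Results are for log-SD 0.5 / 0.8 / 1.0, 8,000 runs per cell.

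| Within-group rule | Raw | Log after exclusion |
|---|---|---|
| 3 SD | 7.4 / 9.1 / 10.6% | 6.2 / 6.0 / 6.6% |
| 2 SD | 10.9 / 10.5 / 10.1% | 8.7 / 8.0 / 8.4% |
| Boxplot, 1.5 IQR | 11.8 / 14.6 / 17.0% | 9.3 / 10.6 / 11.7% |

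Pooled versions of all three rules gave 4.3–5.4%, raw or log. A Mann-Whitney test after the within-group 3-SD rule gave 5.1–5.8%. Log data without exclusion gave 4.9–5.0%.

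**The case against.** The strongest reply is that the SAP has no rule to criticise. It does not say that outliers are defined on outcome values, nor within group, and technical outliers in ECG, EGG or EEG recordings are not ruled out. This stands: both readings are inferences, and the defect is that the criterion is missing.

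A reader might infer that the two lines on exclusion and on the subjects included contradict each other. The documents do not support that. The second line comes later in the same staged list and can mean those who remain after the first stage. It is undefined.

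A reader might also infer that this plan doubles or triples its false-positive rate. That is not established either. A fixed, single-pass pooled rule leaves the rate near 5%. The SAP also provides for transformation or non-parametric tests, which lower the within-group figures considerably. A near-tripling from one pass needs a within-group rule, strong skew and untransformed data together. Nor do the documents show that the people removed would be the best responders.

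What the reply does not remove is that the SAP excludes none of the unfavourable options, and that a log transformation after within-group exclusion still leaves about 6–12%.

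**Conclusion.** The concern holds in conditional form. Whole participants are excluded first, with no criterion, scope, blinding or all-participants analysis, and the analysis set is undefined. At a nominal 5% with 40 versus 10, the rate is:

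- near 5% under one fixed pooled pass;
- about 6–12% under one within-group pass followed by log transformation;
- about 7–18% under one within-group pass on untransformed skewed data (the mildest ANOVA cell, at log-SD 0.5, was 5.6%);
- up to about 31% if within-group exclusion is repeated, and up to about 38% if the rule is picked after seeing results.

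These figures rest on assumed lognormal data and an assumed visit correlation. The missing criterion and the undefined analysis set do not depend on those assumptions. The change should be made; confidence is medium because the rule that would actually be used is unknown.

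**What to change.** Replace the first stage with text to this effect:

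- The primary analysis includes all participants with data, and the SAP defines that set in place of the present line on subjects included.
- No participant is removed for an extreme outcome value. A recording is excluded only for a documented technical or artefact reason, judged without knowledge of group and session.
- HF and other spectral power are log-transformed before any screening.
- Exclusions and their reasons are reported by group.
- Any outlier-excluded analysis is a sensitivity analysis, using one prespecified rule pooled over both groups and applied once.

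A prespecified, group-blind pooled rule on transformed data would also control the error rate. Keeping everyone in the primary analysis is preferred because it needs no threshold and leaves the 10 controls intact.

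Cost: SAP wording and one extra run. Intervals may be slightly wider if genuine extreme values stay in.

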 - Regressions or the Pearson correlations will be performed in order to measure the inter-signal correlation (ECG-EGG-EEG)
 - Regressions or the Pearson correlations will be performed in order to test our hypothesis about the HF/RMSSD related to the "low vagal tone" profile will be more correlated to Δ HF/RMSSD related to the "low vagal flexibility" profile than to Δ HF/RMSSD related to the "high vagal flexibility" profile. As the same as HF/RMSSD related to the "high vagal tone" profile will be more correlated to Δ HF/RMSSD related to the "high vagal flexibility" profile than to Δ HF/RMSSD related to the "low vagal flexibility" profile

Additional analyses

- We will control the age effect and the gender effect.
- Some additional statistical analyses will be exploratory: stability of the resting and the dynamical neurovegetative endophenotypes before the control period (T1) and at the end of the control period (T2).
- Correlation between the LF 0.1Hz and the clinical outcomes.
- To confirm the physiological effects of the BFB (BFB vs pseudo-BFB) on the flexibility of the electrophysiological coupling concerning the brain-visceral axis.

Sample

Power analysis (G * Power; Faul et al., 2007) was performed to determine a priori the sample size needed for this study. The power analysis, for an ANOVA (repeated measures, within-between factors), was performed for an effect size (η_p^2) of .12 with a power of .95 on the main judgment criterion (HRV – vagal tone HF) and reported a necessary sample of at least 22 participants (Kudo et al., 2014; Paul & Garg, 2012; Wells et al., 2012). We decided to include at least 25 IBS patients SII (20 test & 5 control) and 22 PNES patients (20 test & 5 control) in accordance with the possible inclusion rate and the duration of the study.

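### The test-selection rule stops short if unequal variances persist after transformation, and it names no fallback test; with 40 versus 10 participants the Group x Time F test may be mis-sized or left without a replacement

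*Combined protocol and SAP*

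**What the plan says.** Part II, Statistical analyses, has the conditions of each test checked and sets a sequence for when they fail. The first step is a transformation meant to improve normality and homogeneity of the residuals jointly. The second step is: "If the normality is failed and the homogeneity is respected, we would execute non-parametric tests". The choice between parametric and non-parametric tests made in this way covers both the main and the secondary criteria.

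Analyse A then plans a repeated-measures ANOVA with three visits (T1, T2, T3) and two groups, followed by contrasts within each group. It also plans a Student comparison, worded as "test for independent samples will be performed on the psychological scores collected in the second session (T2"; its purpose is to compare the groups' psychological state before the intervention. Analyse B uses Student tests between two cluster-defined groups.

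Part I sets the group sizes by order of entry. For the BFB arm it states: "The first 40 participants (20 IBS / 20 PNES) will be included into the experimental group (BFB training". The control arm is filled from the end of recruitment and is a quarter of that size: "whereas the last 10 participants (5 IBS / 5 PNES) will be included into the control group (no training". The Sample section bases the study size on the same type of model, and the calculation "was performed for an effect size (η_p^2) of .12 with a power of .95 on the main judgment criterion (HRV – vagal tone HF".

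The SAP names no Welch, unequal-variance, robust or permutation method, no particular non-parametric test, and no sphericity correction.

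**The concern.** The sequence leaves two gaps.

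- **Variances still unequal after transformation.** The text gives no next step, whether or not normality holds. The only named tests are then the pooled-variance ANOVA and the Student test. These tolerate unequal variances when groups are of equal size, but not at 4:1.
- **Normality fails, homogeneity holds.** The text moves to non-parametric tests without saying which. Rank tests within one group, or between groups at a single visit, do not address whether the groups change differently over time. The main comparison could therefore go unanswered on this route.

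At stake is the error rate of the Group x Time test on the main criterion (HF). If the ten controls vary more within person than the BFB group, a BFB effect is declared too often. If they vary less, the test becomes very conservative and a real effect is easily missed.

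**Working it through.** **Inputs from the documents.** Groups of 40 and 10 (part I); 2 groups x 3 visits (Analyse A); alpha 0.05 (Statistical analyses); partial eta squared 0.12, power 0.95 and N of at least 22 (Sample). **Assumed, because not given:** all SDs, the correlation between visits, and the sphericity parameter.

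**1. The plan's own figure.** The plan "reported a necessary sample of at least 22 participants". For the within-between interaction:

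- f² = 0.12/0.88 = 0.136
- lambda = f² x N x m/(1 - rho) = 0.136 x 22 x 3/(1 - 0.5) = 18.0, with assumed rho = 0.5 and epsilon = 1
- df = (2-1)(3-1) = 2 and (22-2)(3-1) = 40; critical F = 3.23; power = 0.964

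The smallest N that reaches 0.95 is 21 (power 0.955), which rounds to 22 for two equal groups. The figure reproduces, but it presumes equal groups and one common variance.

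**2. Why 4:1 matters.** Let r be the control/BFB ratio of the variance of within-person change, with BFB variance 1. The true variance of the difference in mean change is 1/40 + r/10. The pooled test estimates it as [(39 + 9r)/48] x (1/40 + 1/10).

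| r | True | Pooled estimate | True/pooled |
|---|---|---|---|
| 1/4 | 0.050 | 0.107 | 0.47 |
| 1/2 | 0.075 | 0.113 | 0.66 |
| 1 | 0.125 | 0.125 | 1.00 |
| 2 | 0.225 | 0.148 | 1.52 |
| 4 | 0.425 | 0.195 | 2.18 |

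At 25 versus 25 both expressions equal (1 + r)/25, so the ratio is 1 for every r.

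**3. Type I error by simulation.** Normal data, no true effect, a subject effect plus within-subject error at three visits, at least 8,000 null trials per setting (20,000 or more for most). The ratio applies to the within-subject error variance at every visit, 40 versus 10.

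| Control/BFB error variance | Group x Time F | Pooled t on T3-T2 | Welch on T3-T2 |
|---|---|---|---|
| 1/4 | 0.2% | 0.5% | 5.1% |
| 1/2 | 1.2% | 1.7% | 5.2% |
| 1 | 5.0% | 4.9% | 5.1% |
| 2 | 13.5% | 11% | 5.2% |
| 4 | 25% | 18% | 5.1% |

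**4. Limits of the effect.**

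- Control SD doubled at T3 only: about 14%. Control SD halved at T3 only: about 3%.
- Only the between-subject SD differs (ratios 1/3 to 3): 4.6% to 5.2%, because the subject effect cancels in the change.
- 25 versus 25, error SD ratio 1/3 to 3: about 5.0% to 5.5%. The allocation drives the problem.
- Greenhouse-Geisser correction at error SD ratio 2: 23.8%, so a sphericity correction does not cure it.
- Mann-Whitney on the T3-T2 change at error SD ratios 0.5, 1 and 2: 1.6%, 4.6% and 10.3%. An ordinary rank test is not a remedy for unequal variances either.
- Skewed errors at SD ratios 0.5, 1 and 2: F test 0.2%, 5.3% and 24.2%; Welch 4.7%, 4.6% and 4.5%.

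**The case against.** **The plan does have a first answer to unequal variances.** A reader might infer that there is no route at all when variances differ. That is not so: transformation comes first and explicitly targets homogeneity. It may well suffice. The gap is only heterogeneity that survives transformation or goes unnoticed.

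**The fallback is not shown to be wrong.** A reader might infer that it cannot test Group x Time. The text does not support this, because no test is named. A rank test on change scores, or a rank-based or permutation method in R (which the SAP lists), would fit the same sentence. What stands is that the choice is open and may leave the interaction untested. Nor should the fallback be blamed for a result that is significant among 40 but not among 10: reading groups separately at unequal n does that just as readily with paired t tests.

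**The 25% is one scenario.** It needs a fourfold within-subject variance in controls at every visit. No SDs are given, and if BFB patients become the more variable group at T3 the test errs on the conservative side.

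**The planned checks would raise the alarm.** Only partly. At 40 versus 10, Levene-type tests flag a twofold variance in about 21% to 27% of trials and a fourfold one in about 64% to 71%. Among trials that pass, the Student error is still about 11% and 21%. When the check does flag and transformation fails, the plan names no next test.

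**Scope.** The T2 Student test is a baseline comparison, so its error rate matters little. Analyse B's group sizes come from clustering and are unknown, so the 40 versus 10 figures do not carry over to it.

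**Conclusion.** The concern holds in limited form. The sequence has no step for unequal variances that persist after transformation, and its non-parametric fallback is unspecified. At 40 versus 10 the planned interaction F test keeps its 5% level only if the variance of within-person change is similar in the two groups. Over assumed error-variance ratios of 1/4 to 4 its type I error runs from about 0.2% to 25%. Unequal spread between subjects does no harm to this test. The actual size and direction of any error cannot be known from the documents. This is an exposure that can be removed cheaply, not evidence that the trial's result will be wrong.

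**What to change.** Before analysis, amend the SAP wording as follows.

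1. Keep the three-visit design, since part I uses T1-T2 as the control period. Name a Group x Time analysis that does not need equal variances, such as a mixed model on T1/T2/T3 with group-specific covariance and small-sample degrees of freedom. Make the between-group T3-T2 contrast the key test, or a Welch test on the T3-T2 change.
2. Name the non-normal alternative on the same change score: a studentised permutation test or Brunner-Munzel. The latter compares the groups by relative ranking rather than by means, so the reported effect should say so.
3. Use Welch instead of Student for the two-group comparisons in Analyses A and B.
4. Delete the condition that homogeneity must hold before non-parametric tests are used. This must go together with item 2, because an ordinary Mann-Whitney test also depends on equal spread under 4:1.

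The cost is SAP text only: no new data, and the methods are available in R. If variances are in fact equal, Welch has about 75% power against 79% for the pooled test at a difference of 1 SD of the tested score.

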BIOFEE SOMATO

Neurovegetative decoupling in the visceral-brain axis and cognitive-emotional vulnerability in somatoform disorders: Interest of vagal biofeedback

BIOFEE-SOMATO

Monocentric study

N° CHU Promoter 38RC20.275

N° ID/RCB : 2020-A02155-34

Version N°1.1- Date: 10/11/2020

Principal Investigator	Pr [name] Hépato-Gastroenterology department, CHU Grenoble Alpes Email : [contact] Tel (direct) : [name] Pole : DIGIDUNE Fonction : Médecin
Promoter	CHU Grenoble Alpes, Délégation à la Recherche Clinique et à l'Innovation [name]

STUDY PROTOCOL & STATISTICAL ANALYSIS PLAN

I : Study protocol

The study requires 3 sessions (T1 / T2 / T3) with at least 24 days between each. The 3 sessions are identical in term of experimental design.

The first session (T1) will start by asking to the participants to answer to 8 self-reported questionnaires (STAI Y-A, PANAS, CES-D, PSS, CFS, VAS, SWLS and ICQ-18) aiming to evaluate the emotional state, the life satisfaction and the acceptance level of pathology.

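### Analysis A's three-session ANOVA drops, for each outcome, any participant without a usable T1, T2 and T3; a mixed model would keep them, for a gain that depends on the pattern of loss

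*Combined protocol and SAP*

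**What the plan says.** Part I (Study protocol) sets the schedule: "The study requires 3 sessions (T1 / T2 / T3) with at least 24 days between each". T1-T2 is the control period and T2-T3 the intervention period. Groups are formed at the end of T2: "The first 40 participants (20 IBS / 20 PNES) will be included into the experimental group", and "the last 10 participants (5 IBS / 5 PNES) will be included into the control group (no training".

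Part II, Statistical analyses, Analyse A, tests the biofeedback effect by "An ANOVA to repeated measurement with an intra factor (measurement time: T1 / T2 / T3) and an inter factor (group: experimental / control", applied to the physiological and psychological data, with contrasts by group to follow. On who is analysed, the same section says only "Analysis will be done on the subjects included", after a step described as "Highlighting outlier participants to exclude from our statistical analysis".

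The Sample section gives a G*Power calculation for a within-between repeated-measures ANOVA. It "was performed for an effect size (η_p^2) of .12 with a power of .95 on the main judgment criterion", which is HF vagal tone, and arrives at 22 participants.

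Neither part contains a rule for a missing or unusable session, an imputation method, a mixed model or an allowance for loss.

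**The concern.** A conventional repeated-measures ANOVA works on complete rows. With three time levels, a participant who lacks one value for an outcome leaves the analysis of that outcome. The intervention contrast lies between T2 and T3, so a participant whose T1 recording fails but whose T2 and T3 are good has that contrast fully observed and is still discarded.

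The control group has only 10 people, so each lost control is costly. Complete-case analysis is also generally valid only under stricter conditions than a likelihood-based mixed model, which tolerates missingness that depends on observed values of the same outcome. The named method therefore gives up precision, and some protection against bias, that software already listed in the SAP could provide.

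**Working it through.** **Inputs from the documents.** 40 experimental and 10 control participants (Part I); three sessions; alpha .05 (Statistical analyses); partial eta squared .12, power .95, N = 22 (Sample).

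**Assumptions, because the documents are silent.** Between-session correlation ρ = .5, sphericity, unit variance, loss completely at random, and a loss rate d of 5% to 20% per session.

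**1. The plan's own figure.** f² = .12/.88 = .1364. For k = 2 groups and m = 3 sessions, λ = f²·N·m/(1−ρ), with df1 = 2 and df2 = 2(N−2). At N = 22, λ = .1364 × 22 × 3/.5 = 18.0 and power is .964. The smallest N reaching .95 is 21, or 22 with equal groups. The stated 22 is thus reproduced, for equal groups and complete data.

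**2. Complete cases under independent loss.** The complete fraction is (1−d)³. At d = .10 it is .729, which leaves 40 × .729 = 29.2 experimental and 10 × .729 = 7.3 control participants. The binomial chance of 7 or fewer complete controls is 54% (16% at d = .05).

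**3. Variance of the group difference in T2-T3 change, at d = .10.**
- Complete cases: 2(1−ρ)/(1−d)³ × (1/40 + 1/10) = 1/.729 × .125 = .1715.
- Mixed model: sum the inverse correlation matrices over the missingness patterns. The expected information per participant has diagonal D = .9(.81 × 1.5 + 2 × .09 × 4/3 + .01 × 1) = 1.3185. The off-diagonal is O = .81(.9 × (−.5) + .1 × (−2/3)) = −.4185. The variance is 2/(D−O) × .125 = 2/1.737 × .125 = .1439.
- Ratio: .1715/.1439 = 1.19.

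**4. The same contrast when the loss is dropout before T3.** Complete cases give a factor 1/(1−d). The mixed model predicts T3 from T1 and T2 (weight 1/3 each, residual variance 2/3), which gives (2/3)/(1−d) + 1/3. At d = .10 the ratio is 1.111/1.074 = 1.03.

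**5. Complete-case power on the plan's effect size.** The λ of step 1 is multiplied by 4 × .8 × .2 = .64 for the 40:10 split, with N = 50(1−d)³. With no loss λ = 26.2 and power is .997. At d = .10, N = 36.45, λ = 19.1 and power is .976.

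| Loss per session | Complete controls | Complete experimental | Variance ratio, independent loss | Variance ratio, dropout before T3 | Complete-case power, independent loss |
|---|---|---|---|---|---|
| 5% | 8.6 | 34.3 | 1.09 | 1.02 | .991 |
| 10% | 7.3 | 29.2 | 1.19 | 1.03 | .976 |
| 15% | 6.1 | 24.6 | 1.31 | 1.05 | .947 |
| 20% | 5.1 | 20.5 | 1.45 | 1.07 | .898 |

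**Sensitivity.** With ρ = .7 the independent-loss ratios are 1.08, 1.18 and 1.42 at 5%, 10% and 20%. Averaging over simulated loss patterns instead of using expected counts gives 1.10, 1.22 and 1.53 at ρ = .5, because chance losses among 10 controls are uneven. Power depends more on ρ: at ρ = .3 the step 5 formula gives .975 with no loss and .909 at 10%, although that ρ does not reproduce the stated 22.

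**The case against.** Much of the opposing case stands.

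- **Deletion is not written into the plan.** A reader might infer that the SAP prescribes listwise deletion. It does not. Deletion follows from the standard form of the named test, and the sentence on analysing included subjects may even intend the opposite. If so, the ANOVA does not deliver that intent.
- **No loss rate is documented.** A reader might infer from long sessions with many sensors that unusable recordings are likely. The documents give no rate, and the loss applies outcome by outcome: a failed EEG or EGG does not remove anyone from the HF analysis, which needs only the ECG. Anyone with a group has also attended T2, so a missed T2 visit cannot arise, though a bad T2 recording can.
- **Not all of the gain needs a mixed model.** At 10% loss, moving from complete cases (.9³) to everyone with both T2 and T3 (.9²) lowers the variance by a factor 1/.9 = 1.11. A plain comparison of T2-T3 change recovers that part; the mixed model brings the ratio to 1.19.
- **Power is not clearly at risk.** A reader might infer that the trial becomes underpowered. On its own effect size, and with the ρ that reproduces 22, it stays at about .95 or above up to 15% independent loss.
- **Bias is only partly addressed.** A model of HF on group and time does not correct for missingness driven by anxiety or symptoms.

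The objection does not remove the central point: the named method discards usable T2-T3 pairs, and nothing else in the plan keeps them.

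**Conclusion.** The point holds as a cheap improvement to the method. It does not show that the planned analysis is invalid. The mechanism is certain for a standard repeated-measures ANOVA; the size rests on assumed loss rates, ρ = .5 and loss completely at random. At 10% of sessions unusable independently, the T2-T3 group contrast has about 19% more variance than under a mixed model, with a range of 9% to 31% for 5% to 15% loss. If loss is mainly dropout before T3, the excess is about 3% at 10%, and the change of method matters little for precision.

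A mixed model would not enlarge the control group of 10, repair its allocation by order of entry, or restore participants removed as outliers. None of these should be read into the recommendation.

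**What to change.** In Analyse A, replace the repeated-measures ANOVA by a linear mixed model for each outcome. Include group, time and group-by-time, an unstructured covariance across the three sessions, Kenward-Roger degrees of freedom, and every usable session. Name the group difference in T2-T3 change as the main contrast.

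Define the analysed set as all participants assigned to a group at T2 with at least one usable recording of that outcome. Requiring assignment at T2 keeps out people seen only at T1, who never received a group. State what makes a recording unusable, and say how the non-parametric fallback treats incomplete sessions, since many rank methods for repeated measures also need complete rows. If missingness is expected to depend on anxiety or symptoms, add those measures to the model.

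The cost is SAP wording. Mixed models are standard in R and SPSS, both already named; confirm that the chosen procedure offers the small-sample correction, which is needed with 10 controls. With complete data the contrast is essentially the comparison of mean T2-T3 changes between groups, so little is given up.
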